8.4 Withdrawal of individual subjects

Subjects can leave the study at any time for any reason if they wish to do so without any consequences. The investigator can decide to withdraw a subject from the study for urgent medical reasons.

8.4.1 Specific criteria for withdrawal

Subjects may be removed from the study if any of the following events occur:

- Significant protocol violation or non-compliance;
- Refusal of the subject to continue treatment and/or observations;
- Decision by the investigator that termination is in the subject's best medical interest;
- Subject changes medication that may interfere with the evaluation of the results;
- Illness during the study period;
- Glucose sensor problems.

8.5 Replacement of individual subjects after withdrawal

A maximum of 2 subjects will be replaced after withdrawal from the study during the training period or before and between the first and second study period. Subjects will not be replaced after withdrawal from the study during one of the study periods.

8.6 Follow-up of subjects withdrawn from treatment

There will no follow-up of withdrawn subjects.

8.7 Premature termination of the study

The study will be put on hold in case of severe hypo-/hyperglycemia during the intervention period until the cause of the severe hypo-/hyperglycemia is determined. Hypo-/hyperglycemia is severe in case it leads to requiring intervention by a third party. The METC will be notified of such event.

9. SAFETY REPORTING

9.1 Temporary halt for reasons of subject safety

In accordance to section 10, subsection 4, of the WMO, the sponsor will suspend the study if there is sufficient ground that continuation of the study will jeopardise subject health or safety. The sponsor will notify the accredited METC without undue delay of a temporary halt including the reason for such an action. The study will be suspended pending a further positive decision by the accredited METC. The investigator will take care that all subjects are kept informed.

9.2 AEs, SAEs and SUSARs

9.2.1 Adverse events (AEs)

Adverse events are defined as any undesirable experience occurring to a subject during the study, whether or not considered related to the investigational product. All adverse events reported spontaneously by the subject or observed by the investigator or his staff will be recorded.

If adverse events occur during the study, the subject has to contact the investigator. If desired, an unscheduled visit could take place. If device deficiencies occur during the study, the subject has to contact the investigator only if it is insulin-related. If there are other technical problems, the patient should follow the regular treatment protocol and contact the customer service of Inreda Diabetic.

9.2.2 Serious adverse events (SAEs)

A serious adverse event is any untoward medical occurrence or effect that

- results in death;
- is life threatening (at the time of the event);
- requires hospitalisation or prolongation of existing inpatients' hospitalisation;
- results in persistent or significant disability or incapacity;
- is a congenital anomaly or birth defect; or
- any other important medical event that did not result in any of the outcomes listed above due to medical or surgical intervention but could have been based upon appropriate judgement by the investigator.

An elective hospital admission will not be considered as a serious adverse event.

The investigator will report all SAEs to the sponsor without undue delay after obtaining knowledge of the events.

The sponsor will report the SAEs through the web portal *ToetsingOnline* to the accredited METC that approved the protocol, within 7 days of first knowledge for SAEs that result in death or are life threatening followed by a period of maximum of 8 days to complete the initial preliminary report. All other SAEs will be reported within a period of maximum 15 days after the sponsor has first knowledge of the serious adverse events.

9.2.3 Suspected unexpected serious adverse reactions (SUSARs)

Adverse reactions are all untoward and unintended responses to an investigational product related to any dose administered.

Unexpected adverse reactions are SUSARs if the following three conditions are met:

1. the event must be serious (see chapter 9.2.2);
2. there must be a certain degree of probability that the event is a harmful and an undesirable reaction to the medicinal product under investigation, regardless of the administered dose;
3. the adverse reaction must be unexpected, that is to say, the nature and severity of the adverse reaction are not in agreement with the product information as recorded in:
 - Summary of Product Characteristics (SPC) for an authorised medicinal product;
 - Investigator's Brochure for an unauthorised medicinal product.

The sponsor will report expedited the following SUSARs to the METC:

- SUSARs that have arisen in the clinical trial that was assessed by the METC;
- SUSARs that have arisen in other clinical trials of the same sponsor and with the same medicinal product, and that could have consequences for the safety of the subjects involved in the clinical trial that was assessed by the METC.

The remaining SUSARs are recorded in an overview list (line-listing) that will be submitted once every half year to the METC. This line-listing provides an overview of all SUSARs from the study medicine, accompanied by a brief report highlighting the main points of concern.

The expedited reporting of SUSARs through the web portal Eudravigilance or *ToetsingOnline* is sufficient as notification to the competent authority.

The sponsor will report expedited all SUSARs to the competent authorities in other Member States, according to the requirements of the Member States.

The expedited reporting will occur not later than 15 days after the sponsor has first knowledge of the adverse reactions. For fatal or life threatening cases the term will be maximal 7 days for a preliminary report with another 8 days for completion of the report.

This is a multicentre study and if a SUSAR occurs in Rijnstate Hospital the coordinating investigator is responsible for the process, and if a SUSAR occurs in Slingeland Hospital or Hospital Gelderse Vallei the principal investigator of that specific centre is responsible for the process.

A description of the method for breaking the code for SUSAR reporting is not applicable because this is not a blinded study.

9.3 Incidents (MDR vigilance definitions)

9.3.1 Incident

Any malfunction or deterioration in the characteristics or performance of the AP system, including use-error due to ergonomic features, as well as any inadequacy in the information supplied by the manufacturer and any undesirable side-effect.

9.3.2 Serious incident

Means any incident that directly or indirectly led, might have led or might lead to any of the following:

- the death of a patient, user or other person;
- the temporary or permanent serious deterioration of a patient's, user's or other person's state of health;
- a serious public health threat.

9.3.3 Non-serious incident

An incident that is not a serious incident.

9.3.4 Recording of incidents

Patients will be referred to the Customer Service of Inreda Diabetic in case of device issues. Device issues of all participants will be recorded. Subsequently, the PMS system and vigilance procedures at Inreda Diabetic will adequately address or resolve and record incidents according to the MDR requirements.

9.4 Annual safety report

In addition to the expedited reporting of SUSARs, the sponsor will submit, once a year throughout the clinical trial, a safety report to the accredited METC, competent authority, and competent authorities of the concerned Member States.

This safety report consists of:

- a list of all suspected (unexpected or expected) serious adverse reactions, along with an aggregated summary table of all reported serious adverse reactions, ordered by organ system, per study;
- a report concerning the safety of the subjects, consisting of a complete safety analysis and an evaluation of the balance between the efficacy and the harmfulness of the medicine under investigation.

9.5 Follow-up of adverse events

All AEs will be followed until they have abated, or until a stable situation has been reached. Depending on the event, follow up may require additional tests or medical procedures as indicated, and/or referral to the general physician or a medical specialist. SAEs need to be reported till end of study within the Netherlands, as defined in the protocol

9.6 Data Safety Monitoring Board (DSMB)

Not applicable.

10. STATISTICAL ANALYSIS

A general description of the statistical methods to be used is given in this chapter, specific details will be provided in the Statistical Analysis Plan. The Statistical Analysis Plan will be prepared before inclusion of the first patient. Deviations from this plan should be reported in the clinical investigation report with a clear statement that this decision was made after preliminary data evaluation and thus post-hoc.

All subjects that completed both study periods will be included in the analysis. Withdrawals will be included in the analysis for adverse events and device deficiencies in order to have an adequate amount of data for analysis. Furthermore, the data collected until their withdrawal will be included in the analysis as well. Carry-over and period effects will be assessed for all parameters.

10.1 Primary study parameter

The proportion of time above range (>10.0 mmol/l) will be compared between Lyumjev insulin and Humalog insulin using a dependent t-test or Wilcoxon signed rank test for paired measurements (significance level of 0.05).

10.2 Secondary study parameters

The pharmacodynamic parameters will be compared between Lyumjev insulin and Humalog insulin using a dependent t-test or Wilcoxon signed rank test for paired measurements (significance level of 0.05).

Pharmacodynamic parameters will be tested for the whole day, daytime and nighttime.

The AP-related parameters will be compared between Lyumjev insulin and Humalog insulin using a dependent t-test or Wilcoxon signed rank test for paired measurements (significance level of 0.05).

10.3 Other study parameters

Demographic characteristics, weight, length and HbA1c will be given as median with IQR.

10.4 Interim analysis

Not applicable.

11. ETHICAL CONSIDERATIONS

11.1 Regulation statement

This study is conducted in full accordance with the principles of the “Declaration of Helsinki” (as amended in Tokyo, Venice, Hong Kong, Somerset West, Edinburgh, Washington, Seoul and Fortaleza) [9], International Standard 14155:2020, this research protocol, the applicable SOPs and the laws and regulations of the Netherlands. The complete text of the “Declaration of Helsinki” is supplied to the investigators upon request. The study shall not begin until the required approval from the Medical Ethical Committee and approval from the CCMO following a marginal review.

11.2 Recruitment and consent

Possible subjects will be approached by his/her treating physician (which may also be the principal investigator). If the subjects indicates to be interested in the study, the treating physician will inform the researcher. The subjects will then be informed by the researcher about the study and will be given enough time to consider participation in the study before signing the informed consent form.

It is the responsibility of the researcher to obtain oral and written informed consent. In obtaining and documenting informed consent, the investigator must comply with applicable regulatory documents and adhere to the ICH GCP guideline [10] and to the requirements in the Declaration of Helsinki (above).

11.3 Objection by minors or incapacitated subjects

Not applicable.

11.4 Benefits and risks assessment, group relatedness

There are no major risks associated with this study since the patients will continue their usual diabetes therapy, in which only the type of insulin is adjusted for 30 days. The most prominent risk is potential altered effectiveness of Lyumjev compared to the currently used insulin, which could lead to hypo- and hyperglycemia, but high and low glucose values will be indicated by alarms given by the AP.

See Chapter 13 for the risk assessment and control measures.

The individual benefit for the participating patients could be improved glycemic control during the study.

11.5 Compensation for injury

The sponsor/investigator has a liability insurance which is in accordance with article 7 of the WMO.

The sponsor (also) has an insurance which is in accordance with the legal requirements in the Netherlands (Article 7 WMO). This insurance provides cover for damage to research subjects through injury or death caused by the study.

The insurance applies to the damage that becomes apparent during the study or within 4 years after the end of the study.

11.6 Incentives

Participants who will participate in the study will be thanked with a gift card of €50,-.

12. ADMINISTRATIVE ASPECTS, MONITORING AND PUBLICATION

12.1 Handling and storage of data and documents

The following data can be recorded directly in to the Case Report Forms (CRFs) using Research Manager and will be collected by Rijnstate Hospital, Hospital Gelderse Vallei and Slingeland Hospital:

- Medical information;
- Demographic characteristics;
- Concomitant medication;
- Adverse events;
- Device deficiencies.

The complete data management process will be described in detail in the Data Management Plan, which will be prepared before inclusion of the first patient.

At the end of the study Inreda Diabetic B.V. collects data from the Inreda AP system of all study participants. This data consists of:

- Glucose measurements;
- Data about insulin and glucagon doses;
- Activity measurements;
- Technical data.

The data from the AP will be exported to a secured computer server, located at Inreda Diabetic B.V. The data is only linked to a study participant number. The database server is secured by authorized access and is password protected. The data at this server can be evaluated for the internal purposes of advancing or improving the device or services for the benefit of future patients, which subjects also sign informed consent for.

Personal data of subjects is available for the researchers to ensure safety. If necessary, monitors or authorities will have access to personal data. Subjects are informed and sign informed consent regarding these procedures.

If the data analysis is performed by Inreda Diabetic B.V., results will be shared with Rijnstate Hospital, Hospital Gelderse Vallei, and Slingeland Hospital.

All of the aspects mentioned above will also be included in the Clinical Trial Agreement (CTA) between Rijnstate Hospital, Hospital Gelderse Vallei, and Slingeland Hospital. The CTA will be agreed upon before the conduct of the study.

12.2 Monitoring and Quality Assurance

An external monitor will be appointed for monitoring. Our first option is the monitor of the APPEL 5 and SMART 1 study: [name] ([name] CSM).

The monitor needs to perform an initiation visit, monitoring visit during the conduct of the study and close-out visit. The monitoring visit during the conduct of the study will be performed when around 4 patients have completed the study.

As a minimum the following requirements apply, verification of:

- 100% of the informed consent forms;
- 100% of the trial subjects (in- and exclusion criteria);
- 10% of the source data;
- Identification and provision of investigational product;
- Use of the correct version of the protocol and procedures.

The monitor needs to set up a monitor plan before the conduct of the study.

In accordance with applicable regulations Inreda Diabetic B.V. may conduct quality assurance audits to ensure processes as defined in the procedures are being carried out as intended.

12.3 Amendments

A 'substantial amendment' is defined as an amendment to the terms of the METC application, or to the protocol or any other supporting documentation, that is likely to affect to a significant degree:

- the safety or physical or mental integrity of the subjects of the trial;
- the scientific value of the trial;
- the conduct or management of the trial; or
- the quality or safety of any intervention used in the trial.

All substantial amendments will be notified to the METC and to the competent authority.

Non-substantial amendments will not be notified to the accredited METC and the competent authority, but will be recorded and filed by the sponsor.

12.4 Annual progress report

The sponsor/investigator will submit a summary of the progress of the study to the accredited METC once a year. Information will be provided on the date of inclusion of the first subject, numbers of subjects included and numbers of subjects that have completed the study, serious adverse events/serious adverse reactions, other problems and amendments.

12.5 Temporary halt and (prematurely) end of study report

The sponsor will notify the accredited METC and the competent authority of the end of the study within a period of 90 days. The end of the study is defined as the last patient's last visit.

The sponsor will notify the METC immediately of a temporary halt of the study, including the reason of such an action.

In case the study is ended prematurely, the sponsor will notify the accredited METC and the competent authority within 15 days, including the reasons for the premature termination.

Within one year after the end of the study, the investigator/sponsor will submit a final study report with the results of the study, including any publications/abstracts of the study, to the accredited METC and the competent authority.

12.6 Public disclosure and publication policy

Publication of the results of this study will be written by the representatives of Rijnstate Hospital, Slingeland Hospital, Hospital Gelderse Vallei, and Inreda Diabetic. The coordinating investigator of Rijnstate Hospital is responsible for the publication and will determine the order of authors.

13. STRUCTURED RISK ANALYSIS

13.1 Synthesis

Both the Inreda AP and Lyumjev insulin are registered and certified products. In this study both products will be used for the intended patient population and within the indication of use. Therefore, section '13.1: potential issues of concern' was omitted.

Lyumjev is not used in combination with the AP. However, Lyumjev is quite similar to Humalog and thus the Inreda AP system seems to be suitable to interact with Lyumjev insulin. Therefore, risks are minimal.

The following safety issues have to be considered.

1. It is unknown if the effectiveness of Lyumjev is completely comparable to the currently used Humalog. This could lead to hypo- and hyperglycemia, but the algorithm of the system will automatically adjust the doses, if applicable. Moreover, high and low glucose values will be indicated by alarms given by the Inreda AP system;
2. Discomfort caused by the new type of insulin. Since Lyumjev induces local vasodilation this could be more painful for the patient compared to injection with Humalog. However, diabetes patients are already familiar with the discomfort of insulin injection. These patients are therefore expected to be able to assess discomfort in advance.

In conclusion, the risks are low and most of the subjects will be already familiar with the mentioned safety issues during the management of their diabetes. The study is therefore classified as low risk. We believe that the investigational product could be an effective successor for the currently used insulin. Besides, in our opinion, the burden for the participants is acceptable.

Revision	D02	Document number:	SAP
	Document title:	FAST-1	
	Status:	APPROVED ON JULY 1, 2025	
	TPL 013.D02	This document is uncontrolled when printed	

Fully Automated glycemic control with ultrarapid insulin in a bihormonal closed loop System in patients with Type 1 diabetes (FAST 1)

Statistical Analysis Plan

Short title	FAST 1
Protocol ID	NL79588.091.22
(Coordinating) Principal Investigator	[name]
Responsible for data management	[name]
Based on protocol version	1.2 (dd 16-06-2022)

Revision	D02	Document number:	SAP
		Document title:	FAST-1
		Status:	APPROVED
		TPL 013.D02	This document is uncontrolled when printed

1 Content

2 Scope.....	3
3 Sample size.....	3
4 Randomization and blinding procedure	3
5 Statistical analysis	3
5.1 Available sets for analysis.....	3
5.1.1 CRF Dataset	4
5.1.2 Artificial Pancreas dataset.....	4
5.2 Statistical analysis program	4
5.3 Standard analysis.....	5
5.3.1 Primary study parameter	5
5.3.2 Secondary study parameters	5
6 Missing data.....	6
7 Interim analysis types	7
8 SAP deviations.....	7
8.1 Description of the deviations from the SAP	7
8.2 Signatures of the people involved in the decisions:.....	8
9 Revision History	9

Revision	D02	Document number:	SAP
		Document title:	FAST-1
		Status:	APPROVED
		TPL 013.D02	This document is uncontrolled when printed

2 Scope

This statistical analysis plan (SAP) applies to the main study of the FAST 1 trial and is developed for the statistical analysis performed by Inreda Diabetic B.V.

3 Sample size

It is hypothesized that the time above range is reduced in subjects using the artificial pancreas (AP) in combination with Lyumjev compared to Humalog. To detect a 3,125% (45 min per day – 15 min per meal) improvement in time spent in hyperglycemia (>10 mmol/l) with a power of 0.90 and alpha of 0.05, 10 subjects are required. To account for drop out of subjects, the sample size will be increased with 2 patients. The sample size calculation has been performed with the program G*Power 3.1.9.4. The percentage time above target range and corresponding standard deviations (SDs) are based on data from the APPEL 5 study.

The following data were used to calculate sample size:

- T-Test: Difference between two dependent means (matched pairs)
- Alpha = 0.05
- Power = 0.90
- Mean 1 = 12.8
- Mean 2 = 9.675
- SD of mean 1 = 3.3
- SD of mean 2 = 3.3
- Correlation = 0.70

4 Randomization and blinding procedure

Block randomization with an equal allocation ratio is used to randomize patients to determine the order of the insulin types (Lyumjev followed by Humalog), and vice versa).

Block sizes of 2, 4 and 6 are used to prevent potential guessing of allocation. Randomization is performed in the electronic CRF (Case Report Forms) of *MyResearchManager*.

No blinding will be applied.

5 Statistical analysis

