8.1 Description of the deviations from the SAP

1. Standard deviation (SD) of the glucose value

- a. Rationale: SD of the glucose value was included as variable because of its added value to indicate glycemic variability.
- b. Detailed description: the SD of the glucose value was added as parameter considering it is a commonly used parameter besides the coefficient of variation and interquartile range of the glucose value to indicate glycemic variability. The SD was calculated for day time, night time and the combination. No data were affected by the addition of this parameter.
- c. Date of decision: May 1, 2023.
- d. People involved in the decision (with signature): [name], [name] and [name].

2. Time below range (TBR) and time above range (TAR)

- a. Rationale: level 1 and level 2 for the TBR and TAR were included in order to report all the important glycemic metrics, following the International Consensus guidelines.
- b. Detailed description: according to the SAP, only the TBR and TAR in total should be calculated (not as separate levels). In addition to the total TBR and TAR, also level 1 and 2 of the TBR and TAR were calculated. These are essential parameters to indicate glycemic control, following the International guidelines on how to report glycemic metrics (Battelino *et al*, Lancet Diabetes Endocrinol (2023)). These metrics were calculated for day time, night time and the combination. These additional parameters had no effect on the data.

Revision	D02	Document number:	SAP
	Document title:	FAST-1	
	Status:	APPROVED	
	TPL 013.D02	This document is uncontrolled when printed	

- c. Date of decision: May 1, 2023.
- d. People involved in decision (with signature): [name], [name] and [name].

3. Exclusion of AP data acquired for five participants

a. Rationale:

A critical procedural error was discovered in the process of data analysis, which led to invalidity of a part of the FCL data. FCL data from the Lyumjev-Humalog sequence (n=5) had to be excluded. Other data from this sequence could still be included (e.g., adverse events). To mention that all FCL data from the Humalog-Lyumjev sequence (n=7) were included.

b. Details on deviation:

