Humalog is used as default insulin in the Inreda AP, and study participants who were randomized to the Humalog-Lyumjev sequence already had their settings optimized for Humalog by the diabetes care team over a long period, considering AP treatment was their regular care at the time. However, in case study participants were randomized to the Lyumjev-Humalog sequence, their settings needed optimization to match with the characteristics of the ultra-rapid insulin Lyumjev. For these participants, the settings of their insulin curve and preinjection were adjusted to take the faster and shorter insulin action into account. These substantial adjustments of the insulin settings during Lyumjev use were not changed back to the Humalog settings that equaled the settings before the start of the study. The Lyumjev-specific Inreda AP settings that were still used after switching back to Humalog affected the glucose regulation of these participants. Therefore, the true impact on glycemic control comparing the insulins within that sequence could not be studied correctly and would have led to invalid outcomes derived from the FCL data. The FCL data obtained in the Lyumjev-Humalog sequence could therefore not be used as valid study data. Only FCL data from the Humalog-Lyumjev sequence were included to determine the outcome parameters (7 of the 12 participants), whereas FCL data from the Lyumjev-Humalog sequence were excluded from further data analysis (5 of 12 participants).

c. Date of decision:

May 4, 2023.

- d. People involved in decision (with signature): [name], [name] and [name].

8.2 Signatures of the people involved in the decisions:

Name (function): [name] (Data specialist)

Signature: 

Name (function): [name] (Lead Clinical Operations)

Signature: 

Name (function): [name] (Clinical project manager)

Signature: 

Revision	D02	Document number:	SAP
	Document title:	FAST-1	
	Status:	APPROVED	
	TPL 013.D02	This document is uncontrolled when printed	

9 Revision History

Rev	Author	Change description	Reviewed by	Approved by	Date
D01	[name]	New document	[name]	[name]	29-08-2022
D02	[name]	Addition of SAP deviations and signatures of people involved	[name]	[name]	01-07-2025

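### The approved SAP revision cuts the primary-endpoint set to 7, below the 10 it says are needed for 90% power, without restating power or precision

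*SAP*

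**What the plan says.** SAP section 3, which matches protocol 4.4, plans for a difference of 3.125 percentage points in time above range and says that "with a power of 0.90 and alpha of 0.05, 10 subjects are required". The inputs are listed there: the design ("T-Test: Difference between two dependent means (matched pairs"), means of 12.8 and 9.675, "SD of mean 1 = 3.3", "SD of mean 2 = 3.3" and a correlation of 0.70. Two patients are added for drop-out, giving 12. Sidedness is not given in that section. Protocol 10.1 specifies only a "dependent t-test or Wilcoxon signed rank test for paired measurements (significance level of 0.05".

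SAP section 8.1 item 3, added in revision D02 (1 July 2025), records a decision of 4 May 2023. It begins: "A critical procedural error was discovered in the process of data analysis". The closed-loop data of the Lyumjev-Humalog sequence (5 participants) were dropped. The result is stated plainly: "Only FCL data from the Humalog-Lyumjev sequence were included to determine the outcome parameters (7 of the 12 participants". Adverse events and other data from that sequence were kept. Time above range is computed from sensor glucose (SAP 5.1.2 and section 6), so the exclusion falls on the primary endpoint.

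Item 3 is silent on power and precision, and section 3 carries no pointer to it. The revision history mentions only the added deviations and signatures.

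**The concern.** One approved document says that 10 participants are needed and that the outcome parameters come from 7. Five were lost where two had been allowed for. The SAP contains a single power figure, 0.90, and nothing tells the reader that it no longer describes the analysed set.

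At stake is how the result is read. If the comparison turns out non-significant, a reader relying on section 3 could treat it as a negative finding from a trial with 90% power and conclude that Lyumjev brings no benefit. Seven participants support that conclusion much less well than the stated design did.

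**Working it through.** **Inputs** (SAP section 3): difference 12.8 − 9.675 = 3.125; both SDs 3.3; correlation 0.70; alpha 0.05; null difference zero.

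**SD of the paired differences:** √(3.3² + 3.3² − 2 × 0.70 × 3.3 × 3.3) = 3.3 × √0.6 = 2.556.

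**Standardised effect:** 3.125 / 2.556 = 1.2225.

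**Power:** non-central t with n − 1 degrees of freedom and non-centrality 1.2225 × √n.

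**Reproducing the plan.** Two-sided, n = 9 gives 0.893 and n = 10 gives 0.929, so 10 is the smallest number reaching 0.90, as stated. One-sided, 8 would be enough (0.927). The two-sided test is therefore inferred from the stated 10.

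**At n = 7.** Non-centrality is 1.2225 × √7 = 3.23. The two-sided critical value on 6 degrees of freedom is 2.447. Power is 0.769.

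| n | Power for 3.125, two-sided | Power for 3.125, one-sided | Difference with 90% power, two-sided | 95% CI half-width |
|---|---|---|---|---|
| 12 | 0.970 | 0.990 | 2.63 | 1.62 |
| 10 | 0.929 | 0.972 | 2.95 | 1.83 |
| 7 | 0.769 | 0.885 | 3.78 | 2.36 |

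The half-width is t(0.975, n − 1) × 2.556 / √n; for n = 7, 2.447 × 2.556 / 2.646 = 2.36. The one-sided difference with 90% power at n = 7 is 3.22. Either way it lies above the 3.125 target. The two-sided type II risk at the target rises from 1 − 0.929 = 0.07 at n = 10 to 1 − 0.769 = 0.23 at n = 7.

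**Variants at n = 7, two-sided:**
- The exact Wilcoxon signed rank test, the plan's alternative, gives about 0.73 by simulation with normal differences.
- Correlations of 0.5, 0.6 and 0.8 in place of 0.70 give 0.56, 0.65 and 0.91.

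**Against the null in SAP 5.3.1.** That null sits at −3.125%, one-sided. At a true reduction of 3.125 points, power equals alpha (0.05) at every n. At a true reduction of 3.78 points and n = 7, the excess over the margin is 0.655 and power is about 0.15. None of the zero-null figures above carries over to that hypothesis.

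**The case against.** The strongest reply is that nothing in section 3 is wrong. It is a design calculation, it reproduces exactly, and later exclusions do not make it false. Keeping it intact and logging the deviation separately is normal practice. This stands: a reader might infer an arithmetic error in the sample size, and there is none. The gap is that D02 reduced the set without stating the consequence.

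Second, a reader might infer that item 3 breaches protocol 10 because it never calls the exclusion post hoc. The documents do not support that. Protocol 10 asks for deviations to be reported "with a clear statement that this decision was made after preliminary data evaluation and thus post-hoc", but places that duty in the clinical investigation report, which is not among the documents. Item 3 supplies what SAP section 8 asks for: rationale, description, date and the people involved. It also discloses that the error surfaced during analysis.

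Third, the exclusion is open. It is listed as a deviation, with 7 of 12 and 5 of 12 written out, so the SAP does not present the reduced analysis as the planned one. The documents report no result either, so any misreading is a risk and not something that has happened.

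Fourth, the two added patients were for drop-out, not for invalidated data. That is true, but the effect on the number analysed is the same.

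Finally, the confidence interval conveys precision better than a power figure recalculated after the event. That is fair, and it is why the interval belongs in the fix. It does not justify leaving 0.90 as the only power figure in the SAP.

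**Conclusion.** The point holds as a failure to restate. The analysed set of 7 is 3 short of the stated requirement, and the loss of 5 exceeds the allowance by 3. On the planning inputs, power for 3.125 points is about 0.77, 90% power needs about 3.8 points or more, and the half-width of the 95% interval is about 2.4 points.

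These figures rest on three assumptions:
- a test against zero difference;
- a two-sided 0.05 level, inferred from the stated 10. If one-sided, power is 0.885 and the 90%-power difference is 3.2, a small shortfall;
- the planning SD and correlation. Power ranges from 0.56 to 0.91 for correlations of 0.5 to 0.8.

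A reader might take 0.77 as the power of the primary test as written. It is not: SAP 5.3.1 sets a one-sided null at −3.125%, to which neither 0.90 nor 0.77 applies. Nor should 0.77 be read as the chance of detecting a treatment effect free of bias. With only the Humalog-Lyumjev sequence left, treatment is confounded with period, which is arguably the larger consequence of the exclusion and is not measured by any power figure.

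**What to change.** Leave section 3 as the planned calculation and add a pointer to section 8.1 item 3. In item 3, state:

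- the analysed number is 7, against 10 required and 12 planned;
- on the planning inputs, power is about 0.77 for 3.125 points, 90% power is reached only from about 3.8 points, and the 95% interval half-width is about 2.4 points (one-sided: 0.885 and 3.2 points);
- these figures are for a zero null and not the −3.125% null of SAP 5.3.1, the two-sided level is inferred from the stated 10, and a single sequence remains, so treatment is confounded with period;
- the paired mean difference will be reported with its 95% confidence interval, and a non-significant result is inconclusive and not evidence of no benefit.

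The post-hoc statement that protocol 10 requires belongs in the clinical investigation report. Repeating the label in item 3 is advisable but not required.

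The cost is wording in the SAP and report. No patients or new data are needed. The stated power becomes less favourable.
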